10. CLINICAL MONITORING STRUCTURE

10.1 Safety Monitoring Plan

The PI will oversee safety of study, including careful assessment and appropriate reporting of AEs, regardless of their clinical significance or their relationship to the study. Subjects will be routinely questioned about adverse events at all study visits. Study related monitoring, audits, inspections by the IRB, DSMB, regulatory bodies and University compliance and QA groups will be conducted. Information about subjects will be kept confidential and managed in accordance with HIPAA. Study data will be

recorded in study progress notes. Explanations will be mandated for any missing data. Study records will be retained according to federal regulations. Subjects will be instructed to seek necessary medical attention and to notify the investigator immediately if they experience any AEs.

10.1.1 Data and Safety Monitoring Board (DSMB)

A DSMB will be assembled by the University of Minnesota's Clinical and Translational Science Institute (CTSI). This DSMB will have at least 3 members, including a statistician, at least one member with previous DSMB experience, and at least one member with relevant clinical expertise and/or experience.

It is the role of the DSMB to protect trial subjects and to provide impartial advice and assistance to the PI regarding the conduct and continuation of the study, so as to protect the validity and credibility of the trial. The DSMB will have access to the clinical protocol, interim data, adverse event reports, clinical monitoring reports, annual and/or progress reports submitted to the IRB and/or regulatory agency, and correspondence between the PI and either the IRB or any Regulatory Agency of competent jurisdiction.

The relationship between the DSMB and the PI shall be an advisory role. The specific roles of this DSMB will be to:

- Assess data quality, including completeness.
- Monitor compliance with the protocol by participants and investigators.
- Monitor recruitment progress and losses to follow up.
- Monitor evidence for treatment differences in the main efficacy outcome measures.
- Monitor evidence for treatment harm (SAEs).
- Advise on protocol modifications suggested by investigators or sponsors.
- Develop and/or monitor clinical trial stopping rules.
- Recommend and/or decide whether trial termination is appropriate.

DSMB members shall disclose potential competing interests, both financial and intellectual. Members shall not use interim trial results to inform trading in pharmaceutical or device company shares or stock in competing companies.

The initial DSMB meeting will occur within the first two months of the study period, prior to enrollment of subjects. At this meeting the DSMB will discuss the protocol and the DSMB charter which includes triggers set for data review or analyses, definition of a quorum, and guidelines for monitoring the study. Guidelines will also address stopping the study for safety concerns and for efficacy based on plans specified in the protocol. At this meeting, the DSMB will also develop procedures for conducting business (e.g., voting rules, attendance, etc.).

The DSMB will then meet at least once annually to examine the accumulated safety and enrollment data, review study progress, and discuss other factors (internal or external to the study) that might impact continuation of the study as designed. The frequency of meetings may be increased if unanticipated adverse events (AEs) or safety issues are observed or enrollment rate exceeds expectations. A DSMB meeting may be requested by DSMB members, study sponsor, industrial collaborator, IRB, or study PI at any time to discuss safety concerns. Decisions to hold ad hoc meetings will be made by the DSMB Chair. Meetings may be held by conference calls or videoconferences or as face-to-face meetings. In the event a DSMB member cannot attend a meeting, he/she may receive a copy of the closed session DSMB report and either participate by conference call or provide written comments to the DSMB Chair for consideration at the meeting.

DSMB meetings will be held in two parts. First, an open section will be held in which demographic data and trial progress will be discussed. Quality assurance and compliance issues may be discussed in this

session, and this session is open to investigators, sponsors, funder, patient advocates, and others as appropriate. Open sessions will be followed by closed sections in which only the DSMB members and specifically invited guests will attend. In closed sessions, the outcomes data will be assessed and recommendations formulated. Closed session meetings may be conducted by teleconference at the discretion of the DSMB Chair.

Meeting notes will be prepared from both the open and closed sessions within 2 weeks of the meetings. The DSMB will not share confidential information, particularly trial interim data with anyone, including the PI. The recommendations of the DSMB will be communicated in writing to the Trial Sponsor, PI, IRB, and/or appropriate regulatory agency. The recommendations open to the DSMB will include the following:

- No action required; continue trial as planned.
- Early termination due to a clear benefit or harm in the interventional group.
- Early termination due to futility.
- Termination of recruitment and/or treatment within a subgroup or single arm of a multi-arm trial.
- Extending recruitment or follow up for all or individual arms of the protocol.

If immediate action is required, the DSMB Chair will personally notify the DAIDS program officer of any findings of a serious and immediate nature or recommendations to discontinue all or part of the trial. In addition to verbal communications, recommendations to discontinue or substantially modify the design or conduct of a study must be conveyed to DAIDS in writing by e-mail, fax, or courier on the day of the DSMB meeting. This written, confidential report may contain unmasked supporting data and include the DSMB member's rationale for his/her recommendations.

11. STATISTICAL CONSIDERATIONS

11.1 Overview and General Design Issues

From the perspective of statistical analysis, the aims of the proposed study are all quite similar: to determine if a randomized intervention has an impact on a longitudinally observed outcome. Despite this similarity, there are differences in the frequency with which some outcomes of interest will be observed and this will impact the details of how the analysis will be conducted. In particular, some variables will be measured quarterly (those that are assessed in peripheral blood, such as LPS, IL-6, TNF and ICAM-1) while those variables assessed via biopsy (such as the number of Ki67+ cells and the magnitude of the FDC pool) will only be available at baseline, and 12 and 30 months after initiating treatment with losartan. The approach that will be used to test for treatment effects in both scenarios will involve fitting mixed models with treatment group indicators, time effects and interactions between time and treatment group to allow for testing for differences in rates of change between the 2 groups. What will differ between the 2 scenarios will be the modeling strategy, as the data that is more frequently observed will permit more sophisticated modeling strategies. These strategies include allowing for nonlinear trajectories via cubic splines and more flexible covariance structures. These models will be fit via restricted maximum likelihood and tests for differences between the treatment groups will be conducted using Wald tests. Standard diagnostics will be employed to assess the adequacy of the fit and remedial measures (e.g. transforming the outcome variable) will be employed as appropriate. The most current version of the statistical software R and the lme package will be used to fit models and examine the data. With 25 subjects per group the study should have adequate power to find strong effects; however losartan has not previously been used in the proposed context.

Analysis of data from the MRI substudy will be descriptive in nature. We are seeking to identify MRI methods that will render an image of the inguinal lymph node that is about to be excised. We will compare

collagen signal by MRI with collagen content measured by trichome stain. Analysis of PK data will include a comparison to previous data collected from HIV infected persons using a similar protocol. We will determine if blood and tissue levels of drug are similar or if they are statistically greater, or smaller than those historical controls.

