11.2 Sample Size Considerations

A previous study of collagen deposition in humans conducted in the [name] lab found a standard deviation for collagen deposition of 0.81 (log scale). We can use this estimate to examine the power of a 2 sample *t*-test to find differences between 2 groups of 25 subjects as this power depends on the magnitude of the difference between the 2 groups.

Difference in average of collagen	0.5	0.6	0.7	0.8
Power	0.59	0.75	0.86	0.94

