11.5 Final Analysis Plan

As detailed in section 11.1, once all of the data is available, mixed effects models will be used to test for differences between treatment groups using standard methods for the analysis of longitudinal data. Conventional significance levels will be used and the fit of the models will be assessed using standard tools (e.g. residual plots).

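### The planned rate-of-change test for biopsy outcomes leaves the baseline means free although biopsies precede randomization: valid, but less efficient than a shared baseline, and matched to the 11.2 power table only under unstated conditions

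*Combined protocol and SAP*

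**What the plan says.** Section 11.1 covers all longitudinal outcomes together. For those measured by biopsy at months 0, 12 and 30, it plans "fitting mixed models with treatment group indicators, time effects". The same model is also to include "interactions between time and treatment group to allow for testing for differences in rates of change between the 2 groups". Models are fitted by restricted maximum likelihood, and "tests for differences between the treatment groups will be conducted using Wald tests". Section 11.5 refers back to 11.1 and adds only that "mixed effects models will be used to test for differences between treatment groups". Neither section fixes the time coding for biopsy outcomes or names one primary collagen contrast. Neither gives the arms a common baseline mean or adjusts for baseline.

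Section 11.2 uses an SD from a previous study in humans, which "found a standard deviation for collagen deposition of 0.81 (log scale". It continues: "We can use this estimate to examine the power of a 2 sample" t-test with 25 subjects per group. The effect row is labelled "Difference in average of collagen", with differences 0.5, 0.6, 0.7 and 0.8 and power 0.59, 0.75, 0.86 and 0.94. It does not say whether 0.81 is the SD of a level or of a change, and it gives no within-person correlation. Section 8.1.2 places the baseline biopsies before randomization on the same visit.

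**The concern.** There are two linked issues.

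The first is efficiency. Because the baseline tissue is taken before allocation, any baseline difference between arms is chance. A model with a free group main effect estimates that difference, and an interaction test subtracts it from the follow-up difference, noise included. With about 25 completers per arm, and repeated node biopsies and colonoscopies for each participant, that information is worth keeping.

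The second is that the power table and the analysis may concern different quantities. A comparison of levels has a variance that does not depend on rho. A comparison of changes does depend on it. A reader of 11.2 therefore cannot tell what power an interaction test would have.

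**Working it through.** **Inputs.** From 11.2: SD 0.81 (log scale), 25 per group, differences 0.5 to 0.8. From 11.1: visits at months 0, 12 and 30; group, time and group-by-time terms. Assumed, because the documents do not give them: two-sided 0.05 (11.5 says only that conventional levels are used), equal variance at each visit, the same correlation rho between any two visits (compound symmetry), 25 complete subjects per arm, and rho from 0 to 0.7.

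**Reproducing the table.** SE = 0.81 × sqrt(2/25) = 0.229. The normal approximation gives 0.588, 0.745, 0.863 and 0.937, which matches all four cells. The exact (noncentral t, 48 df) values are 0.571, 0.728, 0.849 and 0.928.

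**Variance relative to the level t-test, if 0.81 is the SD of a level.**
- Change from baseline to month 30, free baselines: 2(1 − rho).
- Month 30 with a shared baseline mean or baseline adjustment: 1 − rho².
- Ratio of the second to the first: (1 − rho²) / [2(1 − rho)] = (1 + rho)/2. The SD cancels, so the ratio holds whichever SD 0.81 is.

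**Power at a difference of 0.7** (printed 0.86, exact t 0.85). SE = 0.81 × sqrt(variance factor × 2/25). Power is from the noncentral t, with 48 df for the change, and 47 df with variance inflated by 1 + 1/46 for baseline adjustment.

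| rho | Factor, change | Power, change | Factor, adjusted | Power, adjusted | Variance ratio |
|---|---|---|---|---|---|
| 0 | 2.00 | 0.56 | 1.00 | 0.84 | 0.50 |
| 0.3 | 1.40 | 0.72 | 0.91 | 0.87 | 0.65 |
| 0.5 | 1.00 | 0.85 | 0.75 | 0.93 | 0.75 |
| 0.7 | 0.60 | 0.97 | 0.51 | 0.99 | 0.85 |

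The change comparison has the tabulated power where 2(1 − rho) = 1, that is, at rho 0.5.

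**Other interaction contrasts** break even with the table elsewhere:
- Mean of months 12 and 30 minus baseline: 1.5(1 − rho) = 1, so rho 0.33.
- Linear slope over 0, 12 and 30 with a linear effect: (900/456)(1 − rho) = 1, so rho 0.49. If the effect is complete by month 12, 0.57. If it appears only after month 12, 0.44.
- Joint 2-df interaction test at a difference of 0.7: about 0.58 for a linear effect, 0.45 for an early or late one.

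**Readings with no shortfall.** If 0.81 is the SD of the change, the table describes the free-baseline change at any rho. If time is coded by visit and the test is the month-30 group difference (group plus group-by-month-30), the variance factor is 1.00 at every rho, as in the t-test.

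**Linear slope with a shared baseline.** This can distort the estimate when the effect is not linear in time. Take a true month-30 difference of 0.7 and rho 0:
- Complete by month 12: 30 × (12 × 0.7 + 30 × 0.7)/(12² + 30²) = 30 × 29.4/1044 = 0.845 (0.773 at rho 0.3). The free-baseline slope gives 30 × 9.8/456 = 0.645.
- Only after month 12: 30 × 21/1044 = 0.603.

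**The case against.** The strongest reply is that no error has been shown. A t-test is a common planning approximation for a longitudinal model. Section 11.2 sets no target power, and 11.1 claims only that "With 25 subjects per group the study should have adequate power to find strong effects". The text of 11.1 says that interactions allow a test of rates of change, not that this is the only test, and 11.5 is no more specific. The calculation also assumes 25 complete subjects per arm. The protocol enrols 63 to obtain 50 completers, and a mixed model would also use partial data from the others.

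Most of this stands. A reader might infer that the trial is underpowered or that 11.2 overstates its power. The documents do not support that: they give neither rho nor the meaning of 0.81, and above the break-even correlation the planned test has more power than printed. Nor do they support saying that plan and table agree only near rho 0.5. That holds for the change to month 30 with 0.81 read as the SD of a level, and not for every test that the model could supply. It would also be wrong to call the planned test invalid.

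The reply does not remove the efficiency point. For an interaction test with free baselines, the gain from sharing the baseline depends neither on what 0.81 measures nor on whether rho is above or below 0.5.

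**Conclusion.** The point holds as a cheap improvement in efficiency and a needed clarification, not as a demonstrated power error. If collagen is tested by an interaction with free baselines, the test is valid but does not use the equality of baseline means that randomization provides. For month 30, using it reduces the variance by 50% at rho 0, 35% at rho 0.3, 25% at rho 0.5 and 15% at rho 0.7. With 0.81 as the SD of a level, the difference detectable with 80% power at rho 0.3 falls from 0.78 to 0.63.

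Baseline adjustment also makes the printed table approximately a lower bound for the month-30 contrast: at rho 0, power at a difference of 0.7 is about 0.84, against 0.85 exact and 0.86 printed. These figures rest on equal variances, compound symmetry and complete data, and on values of rho that the documents do not supply.

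**What to change.** 1. For collagen, keep the REML mixed model and code time by visit (0, 12, 30). Give both arms one common baseline mean by dropping the group main effect and keeping group-by-visit, or adjust for baseline collagen. Take the contrast from the visit-specific effects.
2. Before unblinding, name the primary collagen contrast. Slope or month 30 remains the sponsor's trade-off. A month-30 contrast makes month 12 supportive, although sections 2.2 and 4.1 list both follow-up biopsies for the primary endpoint. A linear slope uses both, but combining it with a shared baseline is not cost-free, because of the distortion shown above.
3. In 11.2, state power for the chosen contrast over a stated range of rho, and say whether 0.81 is the SD of a level or of a change. If the laboratory has earlier paired biopsies, they could supply rho.

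The cost is an SAP edit and one model term, with no new data, visits or subjects. Baseline adjustment uses one degree of freedom, about 0.01 of power if rho is near 0.

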4. STUDY DESIGN

4.1 Description of the Study Design:

This is a randomized, double-blind, placebo-controlled trial of 50 HIV-1 infected individuals on stable ART randomized in a 1:1 ratio to losartan (50 mg orally daily titrated to 100 mg daily) vs placebo for 30 months. We plan to enroll a total of 63 HIV infected subjects to ensure that 50 complete the protocol. All HIV infected subjects will undergo biopsies of inguinal lymph node (LN) and gut associated lymphatic tissue (GALT) for primary endpoint analysis at baseline, 12 and 30 months after study enrollment. Blood will be collected at least quarterly throughout the study and an intensive blood pharmacokinetic (PK) study will be conducted at month 1. All HIV infected subjects will be vaccinated with the quadrivalent human papillomavirus (HPV) vaccine at months 23, 25 and 29.5. 5 HIV uninfected control subjects will also be enrolled. They will not receive study agents or HPV vaccination and will undergo blood draw and inguinal LN biopsy at one time point only. We anticipate completing subject enrollment over a 14 month period and plan to complete all subject follow up 44 months after the first subject is enrolled.

4.2 Study Endpoints:

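### Uncorrected Wald tests with about 25 subjects per arm can reject too often for the serial blood outcomes, by an amount set by a covariance choice the plan leaves open

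*Combined protocol and SAP*

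**What the plan says.** Section 11.1 gives one analysis approach for all longitudinal outcomes. It uses mixed models with treatment, time and "interactions between time and treatment group to allow for testing for differences in rates of change between the 2 groups". On estimation: "These models will be fit via restricted maximum likelihood". On inference: "tests for differences between the treatment groups will be conducted using Wald tests". On software: "The most current version of the statistical software R and the lme package will be used to fit models".

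Blood outcomes are described as quarterly, and for these the plan adds "allowing for nonlinear trajectories via cubic splines and more flexible covariance structures". Biopsy outcomes have three time points: baseline, 12 and 30 months.

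On size, section 11.1 says "With 25 subjects per group the study should have adequate power to find strong effects". Section 11.5 adds only "Conventional significance levels will be used" and a check of model fit with tools such as residual plots.

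Neither section names a covariance structure, the spline degrees of freedom, a denominator-df method, or a likelihood-ratio, bootstrap or permutation alternative.

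**The concern.** A Wald test refers the squared standardised estimate to a chi-square distribution (or a normal, for one parameter). That is correct only if the covariance matrix is known. Here it is estimated from about 50 people. Two things are ignored: the sampling error in the estimated variance, and the extra variability of the treatment estimates because their weights also depend on the estimated covariance. Both grow with the number of covariance parameters and with the number of effects tested jointly.

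The plan pairs this test with the features that make the error worse. A spline-by-treatment interaction has several degrees of freedom. A fully flexible covariance has 11×12/2 = 66 parameters for 11 visits and 14×15/2 = 105 for 14.

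At stake are the p values and confidence intervals for the serial blood markers of immune reconstitution and activation. There are many of these, so extra error on each raises the chance of a spurious finding that losartan lowers inflammation.

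**Working it through.** **Inputs.** 25 per arm (section 11.1), "randomized in a 1:1 ratio to losartan" or placebo (section 4.1). SD 0.81 on the log scale (section 11.2). Enrolment of 63 to leave 50 completers (sections 2.2 and 4.1). Three biopsy times.

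Blood times: a strict three-monthly grid from 0 to 30 gives 11, an idealisation because visits fall at months 23 and 25 rather than 24. The serum and plasma/PBMC rows of Table 1 (section 8.2) give Day 0, Month 1, seven visits from Months 3 to 27, and Months 12, 23, 25, 29.5 and 30: 1+1+7+5 = 14.

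*Assumptions, because the plan is silent:* two-sided 0.05, complete data, normal errors, spline interaction of 3-6 df.

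**Step 1: the plan's own figures.** Power = Φ(d / (0.81·√(2/25)) − 1.96), with standard error 0.81 × 0.2828 = 0.2291. For d = 0.5, 0.5/0.2291 − 1.96 = 0.222, so power is 0.588. The other differences give 0.745, 0.863 and 0.937. These match the printed 0.59, 0.75, 0.86 and 0.94, which supports two-sided 0.05. The plan states no type I error for its Wald tests, so there is none to reproduce.

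**Step 2: exact size, saturated time, unstructured covariance.** With complete data the Wald statistic is Hotelling's T² on p contrasts with ν = 50 − 2 = 48. Its true size is P(F(p, ν−p+1) > c·(ν−p+1)/(p·ν)), where c is the 95% chi-square point on p df.

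| Test | p | c | F threshold | True size |
|---|---|---|---|---|
| One contrast | 1 | 3.841 | 3.841 | 5.6% |
| Biopsies, 3 visits | 2 | 5.991 | 5.991×47/96 = 2.933 | 6.3% |
| 11 blood visits | 10 | 18.307 | 18.307×39/480 = 1.487 | 18.1% |
| 14 blood visits | 13 | 22.362 | 22.362×36/624 = 1.290 | 26.3% |

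**Step 3: spline mean, unstructured covariance.** Simulated null trials (8,000 per setting, REML in closed form) with spline interactions of 3-6 df rejected in 16-18% at 11 visits and 22-26% at 14. Reducing the mean model to a spline does not remove the excess, because the covariance still has 66 or 105 parameters.

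**Step 4: low-parameter covariance, correctly specified.** With a 4-df spline and 1,500 simulated trials each: random intercept 5.7%, intercept plus serial correlation 5.8%, random intercept and slope 6.7%. The Monte Carlo standard error is about √(0.057×0.943/1500) = 0.6 points, so the first two are not distinguishable from 5%. With random spline coefficients, the Step 2 formula at p = 3 and p = 4 gives 7.2% and 8.1%.

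**Step 5: what repairs the unstructured case.**
- Within-subject denominator df of the lme type leave 17.5% (11 visits) and 25.7% (14 visits) for the saturated test.
- For the 3-df spline test, a Satterthwaite-type F(3, 48) reference leaves about 14-15% and 20%.
- Correcting both the variance of the estimates and the df returns about 5%.

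**Step 6: is a simpler covariance enough?** Not if it is wrong. Fitting a random intercept when slopes also vary gave 8.9%. When the truth had serial correlation, a random intercept gave 26.3% and a random intercept and slope gave 20.9%.

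**The case against.** The strongest objection is that the plan never says unstructured. It says mixed models fitted with lme, for which random effects are a natural reading, and flexible covariance is something the denser data would permit, not a commitment. On that reading the error is about 6-8%. This stands. The 16-26% figures describe a choice that the plan allows, not one it has made.

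Second, section 11.1 says quarterly, so 11 visits is the closer reading and 14 needs every plasma/serum draw in Table 1. This also stands, and is why both are shown.

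Third, a reader might expect dropout to shrink the trial to 20 per arm, where the unstructured figures reach 30-35% at 14 visits. The documents do not support that. They enrol 63 so that 50 complete (50/0.80 = 62.5), so 25 per arm already allows for 20% loss, and REML also uses partial data. If all 63 contributed complete data, the 3-df spline figures would fall to about 14% (11 visits) and 17% (14 visits).

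Fourth, a reader might carry the inflation over to all of secondary endpoints 1 and 2, or to the primary. Section 4.2.2 shows that much of those endpoints is tissue histology and staining, with at most three time points. Table 1 places the HPV vaccine response at month 30. Only the serum, plasma and PBMC measures are exposed.

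It cannot be argued that the default software output already deals with the problem: Step 5 shows that it hardly changes the unstructured result.

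**Conclusion.** The point holds as a conditional one. Section 11.1 commits to a large-sample test in a small trial and leaves open the choice that decides how much this matters. At 50 subjects and nominal 5%, the type I error for the serial blood outcomes is about 6-8% with correctly specified low-parameter random effects. With an unstructured covariance it is about 16-18% (11 visits) to 22-26% (14 visits). For the three-visit biopsy outcomes, including the primary, it is about 6%, which would not change a conclusion.

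A reader might infer that one in five null blood comparisons will be declared significant. The documents do not support that as a forecast, because no covariance structure is named. They do support saying that nothing in the plan prevents it, and that the structure could be chosen after the data are seen.

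The figures rest on complete data, normal errors, two-sided 0.05 and spline interactions of 3-6 df. The change is worth making because it is cheap and protects the secondary inference. It does not call the primary analysis into question.

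**What to change.** In sections 11.1 and 11.5, replace the Wald tests with F and t tests using the Kenward-Roger method, which adjusts both the covariance of the estimates and the denominator df. Satterthwaite or default lme df alone should not be accepted if the covariance is unstructured. Kenward-Roger is itself an approximation, so some excess may remain with 14 unstructured visits. That is a further reason to settle the model in advance.

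For the quarterly outcomes, state before unblinding which visits enter the model, the spline df and knots, and the covariance structure, with a named fallback if it does not converge. Do not simply cap the covariance at a random intercept or similar: a structure that is too simple gave 9-26% in Step 6.

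The cost is SAP wording and a different R function, with no new data, visits or subjects. P values become somewhat larger, and noticeably larger if an unstructured covariance is kept.

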
Though there are no known or anticipated drug interactions between losartan and ARVs, this has not been extensively studied. Therefore an intensive pharmacokinetics experiment will be conducted on all HIV infected subjects at month 1 of the study (when losartan is at steady state). In addition, levels of ARVs and losartan in plasma and PBMCs will be performed quarterly over the 30-month study period and intracellular levels of losartan and ARVs will be measured in LT at month 30. These analyses will be performed in semi real-time to ensure that subjects are not put at risk from unexpected drug-drug interactions.

We will enroll 5 HIV uninfected subjects who will not be randomized to a treatment arm and will not be given HPV vaccination. They will undergo a blood draw and inguinal LN biopsy at one time point only. We will enroll an additional 5 HIV uninfected subject who will not be randomized to a treatment arm nor given HPV vaccine. These 5 subjects will be given Stribild and Prezista for two weeks. In previous studies with HIV-positive individuals, we have shown lymph node concentrations of all ARVs to be suboptimal. No one has yet measured ARV concentrations in lymph nodes of healthy volunteers; we feel this is an excellent opportunity to answer that question. These subjects will return to the medical center for an inguinal LN biopsy and colonoscopy and blood draws at baseline, hours 1, 2, 3, 4, 6, 8, 12 and 24 at one time point only. The five control subjects who are taking Stribild and Prezista will be part of the MRI-sub-study (See Appendix I). This test will occur once during the two weeks while they are taking the antiretrovirals, prior to the biopsy.

In addition, these negative controls are important to the success of the two-photon microscopy experiment, which is used to measure motility of lymphocytes on the LN FRCn. The HIV negative control group will be

used to determine normal motility and samples obtained from HIV infected subjects on losartan and placebo will then be compared to these results. We have preliminary data from similar experiments conducted in mice to suggest that 10 control subjects will be adequate to establish normal motility.

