3.3 Exploratory Objectives

1. Assess the impact of losartan on frequency of dendritic cell and CD4 T-cell interactions with the FRCN using two-photon microscopy.
2. To develop methods to image collagen content of inguinal lymph nodes using MRI
3. To measure drug levels and pharmacokinetic (PK) profile of antiretrovirals in lymph tissues of HIV uninfected people.

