8.4.3 Study Visit(s)

If subject agrees to participate in the trial they will return to the MCRU to receive Stribild and Prezista. The subjects will take these medications for two weeks and return to be seen by the designated study staff. At this time a review of the medical history with the participant and a targeted physical exam will be performed. Blood will then be drawn for CD4, plasma, serum and PBMCs. Inguinal LN biopsy with colonoscopy with ileal and rectal biopsies will be performed. During this time blood draws will be taken at baseline and hours 1,2,3,4,6,8,12, and 24 post-drug administration. The subject will remain at the

MCRU for 12 hours for monitoring. They will then return to the MCRU the following morning for one additional blood draw at 24 hours after drug administration. They will complete the off-study form prior to discharge from the MRCU. Subjects will be instructed to report any subsequent event(s) within 3 months of study completion that the subject, or the subject's personal physician, believes might reasonably be related to participation in this study.

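### The PK comparison with historical data gives no criterion for calling drug levels similar, so with what appear to be five controls a non-significant test could be read as similarity

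*Combined protocol and SAP*

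**What the plan says.** Section 11.1 gives the only analysis text for this comparison: "Analysis of PK data will include a comparison to previous data collected from HIV infected persons using a similar protocol". The next sentence sets out the possible conclusions: "We will determine if blood and tissue levels of drug are similar or if they are statistically greater, or smaller than those historical controls". Nothing in section 11 defines *similar*. No test, PK parameter, historical sample size or variability is given for the comparison. Section 11.5 refers only to conventional significance levels, and does so for the mixed models.

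Section 11.1 does not name the group that supplies the new data. Section 2.2 describes five additional HIV-uninfected controls: "These 5 subjects will be given Stribild and Prezista for two weeks". It says that earlier studies in HIV-positive people found suboptimal lymph-node concentrations, and adds: "No one has yet measured ARV concentrations in lymph nodes of healthy volunteers; we feel this is an excellent opportunity to answer that question". Section 3.3 lists the matching exploratory objective: "To measure drug levels and pharmacokinetic (PK) profile of antiretrovirals in lymph tissues of HIV uninfected people". Section 8.4.3 has these controls undergo lymph-node, ileal and rectal biopsies, with intensive blood sampling: "During this time blood draws will be taken at baseline and hours 1,2,3,4,6,8,12, and 24 post-drug administration".

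**The concern.** A test that fails to reach significance shows that a difference was not demonstrated. It does not show that the levels are alike. Where the only outcomes are *greater*, *smaller* and *similar*, and the first two require significance, *similar* absorbs every inconclusive result. With very few subjects that category can hold sizeable true differences.

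What is at stake is how one exploratory result is worded. Five healthy volunteers take two weeks of antiretrovirals and undergo a lymph-node biopsy and a colonoscopy, for a measurement that the protocol says has not been made before. A report that their tissue levels are similar to those in HIV-infected people would be taken as a finding, even if the data were too sparse to support it.

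**Working it through.** **Inputs from the documents.** Five uninfected controls (section 2.2); a comparison in either direction (section 11.1). The plan gives no power figure for the PK comparison. Its only one is for collagen in section 11.2 (25 per group, SD 0.81 on the log scale, power 0.59, 0.75, 0.86 and 0.94 at differences 0.5 to 0.8). A normal approximation at two-sided 0.05 gives 0.588, 0.745, 0.863 and 0.937, so that table reproduces. It does not bear on the PK question, and the collagen SD cannot stand in for a PK SD.

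**Assumptions, not in the documents.** Two-sided alpha 0.05; a two-sample t-test on log concentrations; *m* historical subjects; a common log-scale SD σ.

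**Formula.** Noncentrality λ = δ / (σ √(1/5 + 1/m)), with m + 3 degrees of freedom. Power is the probability that the noncentral t falls outside the two-sided 5% critical values. The chance of a non-significant result is 1 − power.

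**Step 1: a true difference of 1 SD (δ = σ), which needs no value for σ.**

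| Historical m | λ | Power | Non-significant |
|---|---|---|---|
| 5 | 1.58 | 0.29 | 71% |
| 12 | 1.88 | 0.42 | 58% |
| 20 | 2.00 | 0.48 | 52% |
| 50 | 2.13 | 0.55 | 45% |
| effectively unlimited | 2.24 | 0.61 | 39% |

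The term 1/5 sets a floor, so more historical data cannot take power above about 0.61. In fold terms 1 SD is exp(0.4) = 1.5 at log SD 0.4 and exp(1.0) = 2.7 at log SD 1.0.

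**Step 2: fold differences against an assumed m = 12.** Here √(1/5 + 1/12) = 0.532. For a two-fold difference δ = ln 2 = 0.693, so λ = 0.693 / (0.4 × 0.532) = 3.26 at log SD 0.4 and 1.30 at log SD 1.0.

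| Log SD | Power, two-fold | Non-significant, two-fold | Power, three-fold | Power, four-fold |
|---|---|---|---|---|
| 0.4 | 0.86 | 14% | 0.998 | >0.99 |
| 0.5 | 0.68 | 32% | 0.97 | >0.99 |
| 0.7 | 0.41 | 59% | 0.79 | 0.94 |
| 1.0 | 0.23 | 77% | 0.49 | 0.68 |

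With 6 or 20 historical subjects, two-fold power over the same SD range runs from 0.18 to 0.91.

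**Step 3: precision with m = 12.** The 90% interval for the ratio is the estimate multiplied and divided by exp(1.753 × σ × 0.532), which is 1.45 at log SD 0.4 and 2.54 at log SD 1.0.

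**Step 4: could five controls show equivalence?** Two one-sided tests at 5% each were taken with a true ratio of 1, m from 5 to 50, and log SD = √ln(1 + CV²).
- Margin 0.80–1.25: power is at most 0.04 at CV 30%, and about 0 at CV 50% or more.
- Margin 0.5–2.0: power is 0.92–1.00 at CV 30%, 0.39–0.85 at CV 50% and 0.06–0.34 at CV 80%.

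The margins and CVs are assumptions.

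**The case against.** The strongest reply is that section 11.1 contains one informal sentence, and it does not say that a non-significant test will be called similarity. That is right: the reading is an inference. It stands because no other criterion for *similar* is given, so anyone applying the sentence has nothing else to apply.

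The five-subject basis is also inferred. The trial collects intensive PK data in all HIV-infected subjects at month 1 and drug levels in lymphoid tissue at month 30. If the sentence meant those data, the missing criterion would remain but the figures above would not apply. Sections 2.2, 3.3 and 8.4.3 make the five controls the likelier target.

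A reader might infer that the rule would return no difference whatever the truth. The figures do not support that. At a log SD of about 0.5 or less, three- to four-fold differences are usually detected, and at log SD 0.4 with 12 historical subjects so is a two-fold difference. A reader might also infer that the protocol sets out to test whether low lymph-node levels are specific to HIV infection. Its wording is to measure drug levels and PK profile in uninfected people; it does not pose that hypothesis.

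Finally, the objective is exploratory, lies outside the randomised comparison, and drives no stated decision. That limits the importance but does not justify the verdict wording. The same section makes the MRI analysis descriptive, and this comparison could be handled in the same way.

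**Conclusion.** The concern holds in a limited form. *Similar* has no criterion, and as written it would collect the non-significant results. If the comparison rests on five controls, a true 1 SD difference falls there in about 39% to 71% of cases for any historical group of five or more. That result depends only on the test and the alpha assumed. The two-fold figures (14% to 77%) also depend on an assumed 12 historical subjects and a log SD of 0.4 to 1.0, neither of which is in the documents. Large differences are therefore at risk of being missed mainly when variability is high or the historical group is small. The effect is confined to one exploratory objective; the primary and secondary endpoints are untouched.

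**What to change.** In section 11.1, replace the three-way verdict with the geometric mean ratio (uninfected over historical) and its 90% confidence interval for each drug and compartment. Name the group being compared, and state the historical sample size. Add that similarity will not be concluded from a non-significant test. If the word is kept, tie it to a margin fixed before the data are seen, require the interval to lie inside that margin, and call other non-significant results inconclusive. With five controls a tight margin is out of reach (Step 4), so estimation alone is the realistic choice.

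The cost is a wording change, with no new subjects or samples. The downside is that most comparisons will be reported as estimates or as inconclusive.
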